### **3. Objective(s) and Endpoint(s)**

Objectives	Endpoints
Primary	

Evaluate the safety and tolerability of AMG 340 when administered as monotherapy.

	

Treatment-emergent adverse events

Treatment-related adverse events

Changes in vital signs and clinical laboratory tests

Determine the maximum tolerated dose (MTD) or recommended phase 2 dose (RP2D) for AMG 340 when administered as monotherapy.

	

Dose-limiting toxicities (DLTs)

Evaluate the pharmacokinetics (PK) of AMG 340 when administered as monotherapy.

	

PK parameters of AMG 340 including, but not limited to:

<math>C_{max}</math>

Time to <math>C_{max}</math> (<math>T_{max}</math>)

Area under the concentration-time curve within a dosing interval (<math>AUC_{0-t}</math>)

Secondary	

Evaluate the clinical activity of AMG 340 when administered as monotherapy.

	

Objective response (OR) per RECIST 1.1

Overall survival (OS)

Progression-free survival (PFS) (radiographic and PSA)

6-month landmark radiographic PFS

PSA response (30%, 50%, 70% and 90%)

	

• Time to progression (radiographic and PSA)

• Duration of response (DOR) per RECIST 1.1

• PSA DOR based on PSA50

• Time to symptomatic skeletal events (SSE)

--	---

Exploratory	

• Evaluate immunogenicity of AMG 340

	

• Incidence of anti-AMG 340 antibody formation

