

• Any abnormal laboratory test results (hematology, clinical chemistry, or urinalysis) or other safety assessments (eg, ECG, radiological scans, vital signs measurements), including those that worsen from baseline, that are considered clinically significant in the medical and scientific judgment of the investigator (ie, not related to progression of underlying disease).

• Exacerbation of a chronic or intermittent preexisting condition including either an increase in frequency and/or intensity of the condition.

• New conditions detected or diagnosed after study treatment administration even though it may have been present before the start of the study.

• Signs, symptoms, or the clinical sequelae of a suspected drug-drug interaction.

• Signs, symptoms, or the clinical sequelae of a suspected overdose of either study treatment or a concomitant medication. Overdose per se will not be reported as an adverse event/serious adverse event unless it is an intentional overdose taken with possible suicidal/self-harming intent. Such overdoses are to be reported regardless of sequelae.

• For situations when an adverse event or serious adverse event is due to mCRPC report all known signs and symptoms. Death due to disease progression in the absence of signs and symptoms should be reported as the primary tumor type (eg, metastatic pancreatic cancer). Note: The term “disease progression” should not be used to describe the adverse event.

• “Lack of efficacy” or “failure of expected pharmacological action” per se will not be reported as an adverse event or serious adverse event. Such instances will be captured in the efficacy assessments. However, the signs, symptoms, and/or clinical sequelae resulting from lack of efficacy will be reported as adverse event or serious adverse event if they fulfill the definition of an adverse event or serious adverse event.

Events NOT Meeting the Adverse Event Definition

• Medical or surgical procedure (eg, endoscopy, appendectomy): the condition that leads to the procedure is the adverse event.

- Situations in which an untoward medical occurrence did not occur (social and/or convenience admission to a hospital).
- Anticipated day-to-day fluctuations of preexisting disease(s) or condition(s) present or detected at the start of the study that do not worsen.

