Duration of Response (DOR) per RECIST 1.1:

DOR is defined as the time from the date of an initial objective response per RECIST 1.1, which was subsequently confirmed, to the earlier of soft-tissue progression per RECIST 1.1 or death. Subjects who have not ended their response at the time of analysis will have DOR censored at their last evaluable tumor assessment by CT/MRI scan. This endpoint only applies to subjects with an objective response per RECIST 1.1.

Duration of PSA Response (PSA DOR):

PSA DOR is defined as the time from the date of initial PSA response (PSA 50), which was subsequently confirmed, to the earlier of PSA progression or death. Subjects who have not ended their response at the time of analysis will have PSA DOR censored on the date of their last PSA measurement. The endpoint only applies to subjects with a PSA response (PSA 50).

Details about the censoring rules are included in [Appendix D](#).

Time to Symptomatic Skeletal Events:

Time to SSE is defined as time from Study Day 1 to the first SSE. Otherwise, SSE is censored at the last dose date of investigational product (AMG 340) or end of safety follow-up date, whichever is later.

A Symptomatic Skeletal Event (SSE) is defined as any of the following which is collected on the **Adverse Events** eCRF:

For Part A of the study, a list of preferred terms will be identified at the time of analysis for what constitutes an SSE.

For Part B: there is a separate event categories to identify them

- A symptomatic fracture which is any adverse event of fracture (ankle, hip, spinal, wrist or other) per CTCAE version 5.0.
- Radiation or surgery to bone.
- Spinal cord compression.

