Time to PSA Progression	The median and other percentiles as appropriate, will be presented using the Kaplan-Meier curve and 95% CI using the Brookmeyer and Crowley (Brookmeyer and Crowley, 1982) method.	Safety Analysis Set

Endpoint	Statistical Analysis	Analysis Set
Time to Radiographic Progression	The median and other percentiles as appropriate, will be presented using the Kaplan-Meier curve and 95% CI using the Brookmeyer and Crowley (Brookmeyer and Crowley, 1982) method.	Safety Analysis Set
Duration of Response per RECIST 1.1	Descriptive statistics will be presented. If more than 10 subjects experience a Radiographic response, then the following will be done. The median and other percentiles as appropriate, will be presented using the Kaplan-Meier curve and 95% CI using the Brookmeyer and Crowley (Brookmeyer and Crowley, 1982) method.	RECIST 1.1 Evaluable Analysis Set – Objective Responders
Duration of Response PSA50	Descriptive statistics will be presented. If more than 10 subjects experience a PSA response (PSA50), then the following will be done. The median and other percentiles as appropriate, will be presented using the Kaplan-Meier curve and 95% CI using the Brookmeyer and Crowley (Brookmeyer and Crowley, 1982) method.	PSA Response Evaluable Analysis Set – PSA Responders
Time to Symptomatic Skeletal Events	Descriptive statistics will be presented. If more than 10 subjects experience a Symptomatic Skeletal events, then the following will be done. The median and other percentiles as appropriate, will be presented using the Kaplan-Meier curve and 95% CI using the Brookmeyer and Crowley (Brookmeyer and Crowley, 1982) method.	Safety Analysis Set

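### The Part B fracture component of SSE is called symptomatic but defined as any fracture adverse event, so an asymptomatic fracture found on a scan counts

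*SAP*

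**What the plan says.** Time to SSE is a secondary endpoint under the clinical-activity objective (Protocol Section 3; SAP 2.1). The protocol names it but does not define an SSE. The definition is in SAP 5.1.2:

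- Endpoint: "Time to SSE is defined as time from Study Day 1 to the first SSE".
- Source: "A Symptomatic Skeletal Event (SSE) is defined as any of the following which is collected on the" Adverse Events eCRF.
- Part A: "For Part A of the study, a list of preferred terms will be identified at the time of analysis for what constitutes an SSE".
- Part B: "For Part B: there is a separate event categories to identify them". Three bullets follow this line: fracture, radiation or surgery to bone, and spinal cord compression.
- Fracture bullet: "A symptomatic fracture which is any adverse event of fracture (ankle, hip, spinal, wrist or other) per CTCAE version 5.0".

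SAP Table 9-1 analyses the endpoint in the Safety Analysis Set with descriptive statistics, and adds a condition for going further: "If more than 10 subjects experience a Symptomatic Skeletal events, then the following will be done". What follows is the Kaplan-Meier analysis.

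**The concern.** The endpoint is meant to capture skeletal events that the patient feels. The fracture bullet asks only that a fracture be an adverse event. It sets no symptom or severity criterion, so the word symptomatic does no work in the derivation, and a programmer following the SAP would count every fracture record.

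This matters here because every subject has repeated CT/MRI of chest, abdomen and pelvis and repeated bone scans (Protocol 8.3.1 and Table 1-3). Imaging of that kind can show fractures that cause no symptoms. Such records would add events or bring the first event forward, and their dates would follow the imaging calendar rather than the clinical course. They would also count towards the threshold that decides whether a Kaplan-Meier estimate is produced.

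**Working it through.** **1. Can an asymptomatic fracture become an SSE?** Follow one record through the documents.

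- A scheduled scan shows a fracture and the subject has no symptoms.
- Protocol Appendix 4 (Section 11.4) admits as adverse events abnormal results of "other safety assessments (eg, ECG, radiological scans, vital signs measurements), including those that worsen from baseline, that are considered clinically significant" in the investigator's judgment, with a parenthesis setting aside findings related to progression of the underlying disease. Symptoms are not required.
- Once on the Adverse Events eCRF, the record meets the SAP fracture bullet.
- With no symptom onset to date it by, the event takes the scan date.

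Nothing found elsewhere blocks this. SAP Appendix D gives censoring rules for the other progression and duration endpoints but has no SSE entry, and Table 9-1 adds no criterion.

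**2. Dating.** Under Table 1-3 scans fall at C3D1, which is 2 × 3 = 6 weeks after the first dose, then every 9 weeks (6 + 9 = 15, 15 + 9 = 24), then every 12 weeks, each ± 7 days. Events found only by scan would cluster near weeks 6, 15, 24 and so on.

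**3. Direction.** The endpoint is the time to the first event, so extra qualifying records can only shorten it or turn a censored subject into an event.

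**4. Size of the effect on the trigger.** The documents give no SSE rate, count or power, so there is no stated figure to reproduce. Inputs:

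- From the documents: up to 60 subjects in Part A, up to 40 in Part B, and a trigger of 11 or more subjects.
- Assumed: true SSE proportion *p*; asymptomatic fractures add *d* to the proportion in Part B only.

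Table 9-1 does not say whether the count is pooled, so both cases are shown. With X_A ~ Bin(60, *p*) and X_B ~ Bin(40, *p* + *d*):

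| *p*, *d* | Expected count, pooled | P(X_A + X_B ≥ 11) | Expected count, Part B | P(X_B ≥ 11) |
|---|---|---|---|---|
| 8%, 0 | 100 × 0.08 = 8.0 | 0.18 | 40 × 0.08 = 3.2 | 0.0002 |
| 8%, 2 points | 60 × 0.08 + 40 × 0.10 = 8.8 | 0.26 | 40 × 0.10 = 4.0 | 0.0015 |
| 10%, 0 | 100 × 0.10 = 10.0 | 0.42 | 40 × 0.10 = 4.0 | 0.0015 |
| 10%, 2 points | 60 × 0.10 + 40 × 0.12 = 10.8 | 0.52 | 40 × 0.12 = 4.8 | 0.006 |

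Two points in Part B is 40 × 0.02 = 0.8 of a subject. Over *p* = 6% to 12% and *d* = 1 to 4 points, the same formulas give pooled changes from 0.04 to 0.06–0.14 at *p* = 6%, and from 0.67 to 0.71–0.82 at *p* = 12%. Part B alone stays below 0.05 throughout.

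Part B alone is not negligible at higher rates. Combining *p* = 20% with an independent extra probability of 2% gives 1 − 0.80 × 0.98 = 0.216, and P(X_B ≥ 11) rises from 0.16 to 0.23. With an extra 10%, 1 − 0.80 × 0.90 = 0.28 gives 0.59.

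**The case against.** - **Scope.** The bullet sits under the Part B line, and Part A, with up to 60 of about 100 subjects, has its own rule. SAP 7.2 also allows for Part B not proceeding, in which case the bullet would govern nobody. This stands. A reader might infer that the whole study is affected and inflate all 100 subjects, moving 0.18 to 0.42 and 0.42 to 0.67. The layout does not support that.
- **A possible filter.** The separate Part B event categories might keep asymptomatic fractures out. Neither document describes such a filter, so this limits certainty about what would happen in practice but does not repair the written rule.
- **Traumatic fractures.** A reader might go further and say that a wrist broken in a fall is wrongly counted because an SSE fracture must be pathological or at a metastatic site. Neither document says so. Such a fracture is skeletal and usually felt, and counting all symptomatic fractures avoids subjective attribution in an open-label, single-arm study. Excluding trauma is a choice to be stated, not an error to be corrected.
- **The entry gate.** An asymptomatic fracture counts only if the investigator judges it clinically significant and records it. This stands, and it means the number of such records cannot be predicted from the documents.
- **Data.** The mandatory adverse event attributes in Protocol Appendix 4 include severity but no fracture cause, metastatic-site or symptom field, and the narrative belongs to the serious adverse event form. This rules out a cheap filter on cause. It does not rule out one on symptoms.

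**Conclusion.** The point holds for asymptomatic fractures in Part B: the written rule classifies them as symptomatic events, and the scan sets their date. For Part A the outcome is open, because the preferred-term list does not yet exist. A list of terms alone could not separate symptomatic from asymptomatic fractures.

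The consequence is modest. This is one component of one descriptive secondary endpoint in a single-arm phase 1 study. The powered hypothesis on objective response, the dose decisions and every figure in the documents are untouched. The effect on the Kaplan-Meier trigger rests wholly on assumed rates, and failing the trigger only leaves descriptive statistics. The reason to act is that the endpoint should measure what its name says, and a correction before database lock is cheap.

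**What to change.** In SAP 5.1.2, replace the fracture bullet with wording such as:

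> *An adverse event of fracture that is symptomatic, identified from the recorded adverse event severity grade or a site confirmation of symptoms. Asymptomatic fractures are not SSEs.*

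Then:

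- Apply the same rule to Part A, and fix its preferred-term list before database lock rather than at the time of analysis.
- Say which grades settle the question and which need site confirmation. Neither document reproduces the CTCAE fracture grades. The grade 1 wording that Protocol Table 6-6 uses for infections covers both no symptoms and mild symptoms, so grade alone may not decide the lowest category.
- State whether purely traumatic fractures count. Give a sensitivity count without those the investigator attributes to trauma, where that information exists.
- Report all fracture adverse events separately as safety data, so nothing is lost.

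The cost is SAP wording, a filter on a severity field already mandatory, and a few site queries, some of them retrospective for Part A. Slightly fewer events will be counted.

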5.2 Study Time Points

Study Day 1:

Study Day 1 is defined as the date of the first dose of the AMG 340 administered to the subject.

End of Treatment:

End of treatment is defined as the date the decision was made to end of AMG 340 as recorded on the End of Treatment Status eCRF page.

End of Study for Individual Subject:

End of study for individual subject is defined as the date of the subject last completed a protocol-specified procedure. The date will be recorded on the End of Study eCRF page.

End of Study:

End of study date is defined as the date when the last subject across all sites is assessed or receives an intervention for evaluation in the study (i.e., Last subject last visit), following any additional parts in the study (e.g., long-term follow-up), as applicable.

Safety follow-up Visit:

Safety follow-up visit is defined as upon permanent discontinuation from the study treatment for any reason, a safety follow-up visit will be performed approximately 90 (+7) days after the end of the last dose of AMG 340 and/or product required therapies. However if subject starts a new line of therapy before 90 (+7) days follow-up visit, safety follow-up will be performed through 30 days post last dose of AMG 340 or until the subject begins a new line of therapy, whichever occurs later.

Long-term follow-up Visit:

Subjects will be followed for survival and/or the commencement of subsequent therapy via clinic visit, telephone, or chart review call every 6 months from the SFU visit for up to a maximum 3 years.

5.3 Demographics and Baseline Related Definitions

Age at enrollment:

Subject age at enrollment will be collected in years reported in the Demographics eCRF.

Baseline:

The baseline is defined as the last non-missing value on or prior to the pre-dose of AMG 340 assessments on cycle 1 day 1.

Change from Baseline:

Change from Baseline is the arithmetic difference between post-dose assessments and Baseline.

Change from Baseline = (Post-baseline Value – Baseline Value).

Percent Change from Baseline:

Percent change from baseline is the arithmetic difference between post-baseline and baseline divided by baseline values times 100.

Change (Percent) from Baseline = [(Post-baseline Value – Baseline Value)/Baseline Value] x 100.

6. Analysis Sets

6.1 Safety Analysis Set

Safety analysis set defined as all subjects who have received at least 1 dose of AMG 340.

6.2 Pharmacokinetic/ [REDACTED] Analyses Set

The Pharmacokinetic (PK) Analysis Set will include all subjects who have received at least 1 dose of AMG 340 and have at least 1 PK sample drawn post dose. These subjects will be evaluated for PK Analysis unless the number of data points required for analysis is not enough, or significant protocol deviations have affected the data, or if key dosing or sampling information is missing. The PK Analysis set will be used to conduct the analysis of PK data, unless otherwise specified.

6.3 Study-specific Analysis Sets

6.3.1 RECIST 1.1 Evaluable Analysis Set

RECIST 1.1 Evaluable Analysis Set is defined as all subjects who have received at least 1 dose of AMG 340, have measurable disease per RECIST 1.1 at baseline, and have the opportunity to be followed for at least 6 weeks from start of AMG 340 treatment. Subjects who stopped disease assessments prior to 6 weeks will be included in this analysis set if the **data snapshot date** is at least 6 weeks after their first study dose date.

This analysis set is used for the analysis of the radiographic-measured endpoints of objective response and duration of response (radiographic).

6.3.2 PSA Response Evaluable Analysis Set

PSA Response Evaluable Analysis Set is defined as all subjects who have received at least 1 dose of AMG 340, have a measurable (i.e., > 0) PSA at baseline, and have the opportunity to be followed for at least 9 weeks from start of AMG 340 treatment. Subjects who stopped disease assessments prior to 9 weeks will be included in this analysis set if the **data snapshot date** is at least 9 weeks after their first study dose date.

This analysis set is used for the analysis of PSA-measured endpoints that are PSA responses, PSA duration of response.

6.3.3 DLT Evaluatable Analysis Set

DLT Evaluatable Analysis Set defined as all subjects who are evaluable for DLTs. A subject is considered DLT evaluable if the subject has completed at least the first full treatment cycle or experienced a DLT during the first treatment cycle. This applies only for dose exploration part.

7. Planned Analyses

7.1 Interim Analysis and Early Stopping Guidelines

Amgen will conduct evaluations of the treatment and outcome of the CRS events treated with siltuximab on an ongoing basis to assess if the threshold for pausing siltuximab treatment has been reached as outlined in the table below. If these stopping rules are met, an adhoc DLRT will be triggered to review safety data and available PK, PD, and efficacy data. If recommended by DLRT, the use of siltuximab will resume. The stopping rules to trigger an adhoc DLRT to review siltuximab treatment use a Bayesian approach proposed by Thall, et al (1995); an adhoc DLRT will be triggered if the posterior probability that the CRS progression to grade 3 rate is greater than 30% is > 80% or the posterior probability that the CRS progression to grade 4 rate is greater than 10% is >80%; or observation of any grade 5 CRS after the event has been treated with siltuximab. The stopping boundaries presented below assume a prior distribution of Beta (0.6, 1.4) for progression to grade 3 CRS and a prior distribution of Beta (0.2, 1.8) for progression to grade 4 CRS. The evaluations could occur more frequently if necessary to address emerging safety concerns. If the triggered ad hoc DLRT coincide with regular DLRT, they may be combined.

Table 7-1. The Criteria for Evaluating the Use of Siltuximab

Number of subjects treated with siltuximab	Trigger DLRM if severity of any CRS event treated with siltuximab progresses to Grade 5	
	Or the number of subjects with severity of CRS progressed to Grade 3 after being treated with siltuximab is	Or the number of subjects with severity of CRS progressed to Grade 4 after being treated with siltuximab is
5	≥ 3	≥ 2
10	≥ 5	≥ 3
15	≥ 7	≥ 3
20	≥ 8	≥ 4
25	≥ 10	≥ 5
30	≥ 12	≥ 5
35	≥ 13	≥ 6
40	≥ 15	≥ 6

CRS = cytokine release syndrome; DLRM = dose level review meeting

7.2 Primary Analysis

The primary analysis will occur 6 months following the enrollment of the last subject in Arm B. The data will be analyzed once they have been entered, cleaned, and locked. **If we do not proceed with Arm B of the study, the primary analysis will be combined with the final analysis.**

7.3 Final Analysis

The final analysis will occur after all subjects have ended the study. The data will be analyzed once they have been entered, cleaned, and locked.

8. Data Screening and Acceptance

8.1 General Principles

The objective of the data screening is to assess the quantity, quality, and statistical characteristics of the data relative to the requirements of the planned analyses.

8.2 Data Handling and Electronic Transfer of Data

The Amgen Global Study Operations-Data Management (GSO-DM) department will receive and store all data to be used in the planned analyses. This study will use the RAVE database and pharmacokinetics, antibody, biomarkers, and central lab data outside of RAVE database. The database will be subjected to edit check outlined in the Data Management Plan (DMP). Additional details will be provided in the DMP and Data Acquisition Requirements Specification (DARS).

8.3 Handling of Missing and Incomplete Data

Subjects may miss specific data points for a variety of causes. In general, data could be missing due to a subject's early withdrawal from the study, a missed visit or inability to evaluate an endpoint at a particular point in time.

In general, the safety analysis set will be used without any imputation for missing data for the primary and secondary endpoints. Missing safety endpoints and antibody data will not be imputed, except for adverse events, concomitant medications, and death date as described in [REDACTED]

PK concentrations that are below the quantification limits will be set to zero when included in the non-compartmental model to compute PK parameters.

Missing or incomplete dates will be listed unless imputed as follows. An incomplete start date of an adverse event or concomitant medication taken will be handled by rules mentioned in [REDACTED]

